## 9.3 STATISTICAL ANALYSES

### 9.3.1 Demographics and Baseline Characteristics

The following information collected at baseline will be summarized descriptively in the Safety analysis population to assess the comparability of treatment groups:

- Demographics
- Medical history
- Concomitant medications
- PD biomarkers

- Measures of endoscopic and histological appearance of mucosa of sigmoid colon

### 9.3.2 Safety Analyses

All safety analyses will be based on the Safety analysis population, with participants grouped according to the treatment received (dose level / dose frequency).

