## **OVERALL DESIGN**

### **Study Design**

- Study WP40161 is a multicenter, randomized, adaptive, and placebo-controlled study to investigate the safety, tolerability, pharmacokinetics (PK), preliminary efficacy, and pharmacodynamics (PD) of multiple ascending doses (MAD) of RO7049665 on top of standard of care (SOC) in participants with endoscopic evidence of moderate to severely active UC. Participants may be enrolled if they have a history of anti-TNF $\alpha$  or anti-integrin therapy but may not be actively treated with these agents during the study.
- Investigator and participant blind.
- Participants within each cohort will be randomized in a 4:1 ratio to receive multiple SC injections of RO7049665 or placebo, respectively. Randomization occurs on Study Day -1, after a maximum 35-day screening period.

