### 4. STUDY DESIGN

#### 4.1 OVERALL DESIGN

Study WP40161 is a multicenter, randomized, adaptive, Investigator and participant blind, placebo-controlled study to investigate the safety, tolerability, PK, PD, and

preliminary efficacy of multiple ascending doses (MAD) of RO7049665 on top of standard of care (SOC) in participants with endoscopic evidence of moderate to severely active UC. The participants, investigators, and site personnel will be blinded to treatment assignments.

Since this is the first clinical study in which RO7049665 will be tested in participants diagnosed with UC and the first study in which multiple doses of RO7049665 will be administered, a dose escalation design will be used.

All participants in the study will have evidence of active disease on endoscopy at screening (MCS  $\geq 5$ , Endoscopy subscore of the Mayo Clinic Score [MCS-ES]  $\geq 2$ , stool frequency subscore  $\geq 1$ , and rectal bleeding subscore  $\geq 1$ ). Participants will be eligible for the study if they are currently receiving non-biologic SOC therapy for UC and have not been treated with any biologic therapy within 3 months (or 5 half-lives, whichever is longer) before the start of screening.

Participants will be randomized in a 4:1 ratio to receive multiple SC injections of RO7049665 or placebo, respectively (approximately 8 on active and 2 on placebo per cohort). Participants will receive their first doses in a staggered manner, with a five-day interval between the *first dose of the first, second, and third participants*. *The fourth participant can receive the first dose 14 days after the first dose of the third participant, at the earliest. There will be a 48-hour interval between the first dose of subsequent participants in each dose level.* Based on emerging data, dose levels may be expanded.

The dosing interval will be every 2 weeks (Q2W), for 4 doses. The first dose level will be 3.5 mg, the second dose level will be 7.5 mg *and participants enrolled in the cohorts of dose level 3 will receive 15 mg of RO7049665 (or placebo).* The doses are based on safety, tolerability, PK and PD data derived from study WP39826 (see Section 4.3) and *review of data from completed cohorts in this study.* Each dose level will have cohorts of approximately 10 participants, randomized in the ratio of 4:1 RO7049665 to placebo. Based on the emerging data there may be more than one cohort enrolled per dose level.

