The second dose level may run in parallel with the first (see Section 1.2), after completion of recruitment into the lower dose level. However, prior to enrolling participants into the higher dose level, there will be an assessment of safety, tolerability, ADA, PK and selected PD data from at least 5 participants (4 on RO7049665, 1 on placebo) in dose level 1 who have received at least 8 weeks of treatment.

An overview of the study design is provided in Section 1.2.

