### **9.2 SAMPLE SIZE DETERMINATION**

The study will enroll up to 65 participants to assess the safety and tolerability of repeated dosing of RO7049665 (approximately 10 participants, randomized in the ratio of 4:1 RO7049665 to placebo, per cohort).

The sample size for this study was selected on the basis of clinical judgment and practicality. It was not determined on the basis of power against a formal statistical hypothesis. However, with a full cohort of 8 participants treated at a given dose level, there is an 83% chance to observe at least one AE that has a true incidence rate of 20% at that dose level in the population. After 4 participants have been treated at a given dose level, there is a 59% chance of observing such an AE.

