### **9.3.4 Efficacy Analyses**

Preliminary efficacy will be evaluated as a secondary objective of the study by comparing between dose groups the following endoscopic and histologic measures of disease activity. Change from baseline to Day 57 will be analyzed and reported descriptively.

- Change from baseline to Day 57 (and descriptively at Day 29) in endoscopic indices of disease activity (Ulcerative Colitis Endoscopic Index of Severity [UCEIS] and MCS-ES)
- Change from baseline to Day 57 (and descriptively at Day 29) in histology score of sigmoid colon biopsies (GS, RHI, and Nancy Histology Index [NHI])

In addition, preliminary efficacy will also be evaluated by comparing overall disease activity between dose groups using:

- Change from baseline to Day 57 (and descriptively at Day 29) in MCS

The main foreseen intercurrent event for this study is early treatment discontinuation. In the scenario that no intercurrent events occur (i.e., all participants complete the expected number of doses), the estimand is uncontroversial as simply the mean difference between treatment groups in change from baseline to Day 57 in efficacy scores. If however, intercurrent events are observed, three different strategies will be employed to handle early treatment discontinuation, each leading to their own respective estimands.

A treatment policy strategy (ITT population) will be used to estimate the difference between dose groups in the change from baseline in endoscopy, histology and overall disease activity scores, regardless of whether early treatment discontinuation occurred. In the absence of missing data, this can be achieved using Analysis of Covariance (ANCOVA) with dose group as a factor, otherwise an imputation method will be applied as appropriate.

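### Safety and efficacy displays group only by dose received, although placebo is randomised within sequential dose-level cohorts; add same-level placebo columns and handle the Day 50 laboratory results separately (minor)

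*Combined protocol and SAP*

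**What the plan says.** **Randomisation and sequence.** The Synopsis (Study Design) states: "Participants within each cohort will be randomized in a 4:1 ratio to receive multiple SC injections of RO7049665 or placebo, respectively". Section 4.1 gives "approximately 8 on active and 2 on placebo per cohort" and adds: "Based on the emerging data there may be more than one cohort enrolled per dose level". Treatment at 7.5 mg may overlap in time with treatment at 3.5 mg, but the higher level opens only "after completion of recruitment into the lower dose level". Section 4.1.2 requires a review of at least 8 weeks of data from 5 participants at the preceding level before escalation. The 15 mg level was added in Version 5, when Section 2.3 could already draw on Cohorts 1 (3.5 mg) to 4 (7.5 mg).

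**Analysis.** Section 9.3.2 bases all safety analyses on the Safety population, with "participants grouped according to the treatment received (dose level / dose frequency"). Table 7 plans listings and descriptive tables, with no cohort factor and no rule for displaying placebo. Section 9.3.4 evaluates preliminary efficacy by "comparing between dose groups the following endoscopic and histologic measures of disease activity". Its ANCOVA and logistic models name dose group as the factor and mention neither cohort nor dose-level period.

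**Differences between levels.** Under Section 1.3 (Table 1, footnote x), Day 50 safety laboratory tests apply only to participants enrolled in dose level 3. The Version 5 rationale also introduces suggested pre-medication after a systemic reaction, a new individual stopping criterion for such reactions and a longer wait before the fourth participant, and removes the regulatory T-cell stopping criterion.

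**The concern.** Randomisation protects the comparison of drug with placebo inside a cohort. A 15 mg group set against placebo participants gathered from all levels loses part of that protection, because most of those participants would have been recruited earlier, under other protocol versions.

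The Day 50 tests make this concrete without any assumption about calendar drift. Incidence of abnormal laboratory findings is a primary endpoint, and eosinophilia is among the most frequently reported adverse events so far (Section 2.2.2.1). The Version 5 rationale says the visit was added so that eosinophils can be followed alongside flow cytometry. Participants at dose level 3 therefore have one more laboratory visit than everyone before them. Same-level placebo shares that visit, since sites are blinded; placebo from earlier levels does not.

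Efficacy has a similar route. A stop after a second systemic reaction is an early discontinuation. That counts as treatment failure in the composite strategy and can remove the participant from the per-protocol population.

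Section 4.2.2 says the placebo arm is there to help judge whether adverse events are drug-related, so the display should use the placebo participants who serve that purpose best.

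**Working it through.** **The plan's own figures.** Section 9.2 gives the chance of seeing at least one event of true incidence 20%. With 8 treated, 1 − 0.8^8 = 0.832 (stated 83%). With 4 treated, 1 − 0.8^4 = 0.590 (stated 59%). Both reproduce and are unaffected by this point.

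**Numbers per level (assumed split).** At the maximum of 65, 4:1 gives 52 active and 13 placebo. Four earlier cohorts of about 10 give 40 participants, hence 40/5 = 8 placebo. The remaining 25 give 20 active and 5 placebo at 15 mg. Dividing the earlier 40 equally gives 20/20/25 by level: active 16/16/20, placebo 4/4/5. The documents fix no split by level. On this one, 8/13 = 62% of placebo participants come from earlier levels.

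**Background drift (assumed rates, no drug effect).** Apparent difference at 15 mg = rate in the level 3 period − pooled placebo rate.

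| Background rate by level | Pooled placebo | 15 mg − pooled placebo |
|---|---|---|
| 20/25/30% | (4×0.20 + 4×0.25 + 5×0.30)/13 = 25.4% | +4.6 points |
| 20/30/40% | (4×0.20 + 4×0.30 + 5×0.40)/13 = 30.8% | +9.2 points |
| 40/30/20% | (4×0.40 + 4×0.30 + 5×0.20)/13 = 29.2% | −9.2 points |
| no change | 20% | 0 |

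Other splits (25/20/20, 20/30/15, 10/40/15) give 4.6 to 5.4 points for a 10-point rise and 9.2 to 10.8 for a 20-point rise. Against same-level placebo the expected difference is 0 in every row.

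**Day 50 visit (assumed per-visit probability).** If each laboratory visit independently shows an abnormality with probability q, one visit added to k raises the incidence by q(1 − q)^k. For q = 0.02 to 0.10 and k = 8 to 10 (assumed, because the schedule table is hard to read in this copy), the gain is 1.6 to 4.3 points with no drug effect. That is the artefact between 15 mg and an earlier level. Against pooled placebo, 5 of 13 also have the visit, so the artefact is 8/13 of the gain: 1.0 to 2.6 points. Against same-level placebo it is 0.

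**Precision.** SE = sqrt(p(1 − p)(1/n_active + 1/n_placebo)) at p = 0.20.

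| Comparison | SE |
|---|---|
| 20 active v 13 pooled placebo | 0.143 |
| 20 active v 5 same-level placebo | 0.200 |
| 16 v 13 | 0.149 |
| 16 v 4 | 0.224 |
| 8 v 2 (one cohort) | 0.316 |

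**Would a stratified overall estimate help?** The Mantel-Haenszel weight for a risk difference is n_a·n_p/(n_a + n_p): 16×4/20 = 3.2, again 3.2, and 20×5/25 = 4.0. As shares of 10.4 these are 4/13, 4/13 and 5/13. Those are also the shares of each level in the crude active rate (16/52, 16/52, 20/52) and in the crude placebo rate (4/13, 4/13, 5/13). With exact 4:1 in every stratum, the stratified and crude differences are therefore identical.

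**The case against.** **Pooling is not stated.** A reader might infer that the plan commits to a single placebo group. It does not. Table 5 gives placebo no dose, which makes pooling the natural reading under grouping by treatment received. However, placebo participants are enrolled in dose-level cohorts and are counted by level in the escalation rule. The firm finding is that the display is unspecified; the bias follows only if placebo is pooled.

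**Nothing is tested.** A reader might also infer that drift will be read as a dose effect on the primary endpoint. Section 9.1 has no hypotheses, Table 7 is descriptive, and the documents show no drift. Escalation reviews use data from the preceding level, so they do not depend on a pooled end-of-study table. This stands: drift could mislead a reader of the tables, but it does not drive a planned decision.

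**The changeover is not clean.** The reaction-management changes follow an investigator letter issued before Version 5, after an event at 7.5 mg. They need not begin at the boundary between dose levels. No mechanism links the longer stagger to event rates, and the documents do not place the start of the pandemic between levels. This also stands, and it leaves the Day 50 tests as the clearest documented difference.

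**Pooling is defensible.** With about 2 placebo participants per cohort, same-level columns are noisy: the SE of 20 points for 20 v 5 exceeds any shift illustrated above. That is a good reason to keep the pooled column, but not to omit the other. Confounding of dose with time is inherent in ascending-dose designs, and no display of placebo repairs the comparison of one active dose with another.

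**Conclusion.** The point holds as a minor one. The randomised unit is dropped from the safety grouping and from the named efficacy model terms, the handling of placebo is not stated, and no comparison with same-level placebo is planned. The Day 50 tests are a documented difference in ascertainment that affects a primary endpoint. Their effect cannot be computed from the documents; under the per-visit assumptions above it is about 1 to 3 points against pooled placebo and about 2 to 4 points between 15 mg and a lower level.

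Any wider drift is of unknown size and sign. The 5- to 10-point shift is an illustration that rests on an assumed change of 10 to 20 points in the background rate, the assumed splits by level, no drug effect and pooled placebo. The documents do not support a claim that such a change has happened. Sample size and the stated detection probabilities are unaffected.

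**What to change.** - **Section 9.3.2, placebo:** state that placebo will be shown both pooled and by dose level, with the same-level placebo column beside each active dose.
- **Section 9.3.2, Day 50:** leave Day 50 laboratory results out of incidence comparisons across doses or against pooled placebo, or tabulate them separately. They remain available for the 15 mg versus same-level placebo display and for individual safety review.
- **Section 9.3.4:** add the same-level placebo contrast for each dose as a descriptive sensitivity display, and note that dose-versus-dose contrasts are not randomised.
- **Do not rely on a stratified overall active-versus-placebo estimate as the remedy.** With 4:1 in each stratum it equals the crude estimate, and it averages over the three doses.

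The cost is analysis wording and a few table columns, with no change to conduct or sample size. The downside is imprecision: about 2 placebo participants per cohort, or about 4 to 5 per level if two cohorts are enrolled. The same-level columns should therefore supplement the pooled column and not replace it.

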**Table 7 Safety Statistical Analysis Methods**

Endpoint	Statistical Analysis Methods
Adverse events	The original terms recorded on the eCRF by the Investigator for adverse events will be coded by the Sponsor. Adverse events will be summarized by mapped term and appropriate thesaurus level.
Clinical laboratory tests	All clinical laboratory data will be stored on the database in the units in which they were reported. Laboratory test values will be presented in International System of Units (SI units; Système International d'Unités) by individual listings with flagging of abnormal results. Summary tables of change from baseline over time will be displayed. See Appendix 4 for details on standard reference ranges and data transformation and the definition of laboratory abnormalities.
Vital signs	Vital signs data will be presented by individual listings with flagging of values outside the normal ranges and flagging of abnormalities. In addition, tabular summaries will be used, as appropriate.
ECG data analysis	ECG data will be presented by individual listings. In addition, tabular summaries will be used, as appropriate.
Concomitant medications	The original terms recorded on the participants' eCRF by the Investigator for concomitant medications will be standardized by the Sponsor by assigning preferred terms. Concomitant medications will be presented in summary tables and listings.
Other	Physical examination results, safety biomarkers and incidence of ADAs will be listed and summarized descriptively.

### 9.3.3 Pharmacokinetic Analyses

PK parameters will be read directly from the serum concentration-time profiles or calculated by using standard non-compartmental methods. The following PK parameters will be computed for RO7049665. However, other PK parameters might be computed in addition as appropriate:

- Time to maximum concentration ( $T_{max}$ ) post the dose on Day 1, and on Day of last dose
- $C_{max}$  post the dose on Day 1, and post the dose on Day of last dose
- Area under the serum concentration-time curve after the first dose administration extrapolated to infinity ( $AUC_{inf}$ ) and over the dosing interval ( $AUC_{tau}$ ) after the last dose administration (where  $\tau=2$  weeks). If deemed useful, a partial  $AUC_{0-t}$  may be used instead of  $AUC_{inf}$  or  $AUC_{tau}$  should extrapolation to infinity or up to  $\tau$  not be considered reliable.

- Apparent clearance after the first dose administration ( $CL/F = Dose/AUC_{inf}$ ) as well as after the last dose administration ( $CL_{ss}/F = Dose/AUC_{tau}$ )
- Apparent volume of distribution ( $V/F$ ) after the first dose administration
- Estimates of  $T_{1/2}$  after the first dose (Day 1) as well as washout after last dose administration

The dose proportionality will be evaluated in an exploratory manner.  $C_{max}$  and  $AUC_{tau}$  (or  $AUC_{0-t}$  if deemed useful) post the dose on Day 1 and  $C_{max}$  and  $AUC_{tau}$  post the dose on Day of last dose will be tested for dose proportionality. This will be done using one way Analysis of Variance (ANOVA) to test the dose effect using dose normalization and a natural log transform.

In addition, to evaluate drug accumulation, individual as well as mean (SD) of apparent peak (12 hour post dose) and trough (predose) after each dose administration will be plotted graphically over the course of assessments as per [Table 2](#). In addition,  $AUC_{tau}$  post the dose on Day 1 will be tested statistically against  $AUC_{tau}$  post the dose on Day of last dose using an ANOVA with terms in the model for participants and day. A natural log transform of the data will be done prior to the analysis.

Individual and mean serum concentrations at each sampling time point for RO7049665 will be presented by listings and descriptive summary statistics including arithmetic means, geometric means, ranges, standard deviations, and coefficients of variation. Individual and mean concentration versus time will be plotted on linear or semi-logarithmic scales as appropriate.

All PK parameters will be presented by individual listings and summary statistics including arithmetic means, geometric means, medians, ranges, standard deviations, and coefficients of variation.

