Immunogenicity was assessed, and positive results for anti-drug antibody (ADA) were observed in a total of 12 participants starting from Cohort 5 (dose of 190 µg). ADAs were of early onset (detected in first samples on Day 8 post-dose), generally transient, and exhibited dose dependency with regard to titers and incidence. The presence of ADA had no apparent impact on the safety, PK and PD profiles. Further analysis was performed and concluded that the ADAs were not capable of neutralizing recombinant human IL-2.

Serum RO7049665 concentration reached peak level ( $C_{max}$ ) approximately 12 hours post-dose and declined in an apparent biphasic manner, with a mean apparent terminal phase half-life of approximately 72 to 137 hours (see [Table 3](#)). Serum exposure levels of RO7049665 were below or close to the detection limit in the 1.5 and 5µg dose groups and thereafter increased with increasing doses in a highly variable manner. Overall, no obvious deviation from dose-linearity was noted. Sufficient concentration data for reliable estimates of non-compartmental parameters in terms of both AUC and  $C_{max}$  was available as of cohort 6 (650 µg) and above (see [Table 3](#)). Although the data showed moderate between-subject variability, no relevant departure from linearity was noted. The mean serum apparent systemic clearance of RO7049665 appeared dose-independent and ranged from 1.4 to 2.2 L/h.

RO7049665 disposition occurred with a mean  $T_{1/2}$  of about 5 days, thus is expected to approach near-complete washout ( $C_{trough} < 10\%$  of  $C_{max}$ ) no later than 2 weeks post last dose. Accordingly, no substantial accumulation in reaching steady state is expected in a biweekly regimen.

At the highest dose of 7500 µg RO7049665, exposure was 33% and 65% of the exposure at the no-observed-adverse-effect level (NOAEL) (established in female monkeys on Day 22) in terms of  $C_{max}$  and  $AUC_{0-168h}$ , respectively.

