**Table 5 Summary of Treatments Administered**

Study Treatment Name:	RO7049665	Placebo
Dosage Formulation:	Solution for injection	Solution for injection
Unit Dose Strength:	5.0 mg/mL	N/A
Dose:	Starting dose 3.5 mg (dose level 1), 7.5 mg (dose level 2), and 15 mg (dose level 3)	N/A
Route of Administration:	SC injection	SC injection
Dosing Instructions:	RO7049665 must be prepared for dosing under appropriate aseptic conditions and should be used immediately. The solution for injection must be filtered prior to use	Placebo must be prepared for dosing under appropriate aseptic conditions and should be used immediately. The solution for injection must be filtered prior to use
Packaging and Labeling:	RO7049665 and Placebo will be provided in 2 mL colorless glass vials. Each vial will be labeled as required per country requirement.	
Storage Conditions	For RO7049665 and Placebo, if not used immediately, the total storage time of the dose solution prior to administration should not exceed 24 hours to limit the risk of microbial growth in case of accidental contamination. The recommended storage condition for the dose solution is 2°C to 8°C, but dose solutions may be stored at room temperature for up to a maximum of 4 hours	
Manufacturer	F. Hoffmann-La Roche, Ltd.	F. Hoffmann-La Roche, Ltd.

Guidelines for dosage modification and treatment interruption or discontinuation are provided in [Section 6.6](#) or [Section 7](#), respectively.

Please see the [RO7049665 Investigator's Brochure](#) and Pharmacy Manuals for more details.

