## **9. STATISTICAL CONSIDERATIONS**

### **9.1 STATISTICAL HYPOTHESES**

Not applicable.

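### Dose proportionality is assessed by an unordered ANOVA test with no between-dose estimate or interval, so a moderate departure can go undetected and a non-significant result would not support proportionality

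*Combined protocol and SAP*

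**What the plan says.** Section 9.3.3 opens the topic with "The dose proportionality will be evaluated in an exploratory manner". It then says that Cmax and AUCtau (or a partial AUC), on Day 1 and on the day of the last dose, "will be tested for dose proportionality", and gives the method: "This will be done using one way Analysis of Variance (ANOVA) to test the dose effect using dose normalization and a natural log transform". That makes four tests. No significance level, slope, ratio between doses, confidence interval or acceptance range is given, and nothing says how the p-value will be read. Section 9.1 (Statistical Hypotheses) reads "Not applicable".

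For accumulation, the same section compares Day 1 AUCtau with last-dose AUCtau on the log scale "using an ANOVA with terms in the model for participants and day", alongside plots of peaks and troughs.

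Other planned output bears on the point. Section 9.3.3 computes CL/F after the first dose and CLss/F after the last, and presents every PK parameter by listings, geometric means and CVs. Section 9.3.7 allows dose-exposure-response modelling but does not require it.

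**The concern.** An ANOVA on log dose-normalised exposure takes proportionality as its null hypothesis. A significant result argues against proportionality. A non-significant one may mean that exposure is proportional, or only that the groups are small and variable, and the p-value does not separate the two. Treating the three doses as unordered categories also spends two degrees of freedom on what is most naturally a one-parameter trend, which costs power against the likeliest kind of departure.

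Multiple-dose PK is the first-listed secondary objective, and Section 2.3 says that the study should characterise the PK/PD relationship to support later dose-setting studies. The 15 mg level is twice the highest dose given in the healthy-volunteer study, so how exposure scales over this range is an open question. A slope with its interval would answer it directly and would show how firm the answer is.

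**Working it through.** **The plan's own figures.** The only probabilities in the plan are in Section 9.2 and concern adverse events: 1 − 0.8^8 = 0.832 and 1 − 0.8^4 = 0.590, which match the stated 83% and 59%. No figure is given for dose proportionality.

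**Inputs from the documents**
- Doses 3.5, 7.5 and 15 mg (Table 5). Range 15/3.5 = 4.29-fold; ln 4.29 = 1.455.
- Active participants: 8 per level for one full cohort (Section 9.2). The maximum is 65 × 4/5 = 52. Section 2.3 refers to Cohorts 1 (3.5 mg) to 4 (7.5 mg). Four cohorts of about 8 active make 32, leaving 52 − 32 = 20 for 15 mg.
- CVs at 0.65, 2.2, 5 and 7.5 mg, n = 6, 6, 5, 6 (Table 3): AUCinf 43.1, 37.7, 26.9, 55.4%; Cmax 49.4, 58.8, 27.4, 85.6%.

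**Assumptions (not in the documents).** Alpha 0.05. Table 3 CVs are geometric. Single-dose variability in healthy volunteers carries over to participants with UC, and AUCinf stands in for AUCtau. No PK exclusions. The larger sizes are split 17/17/17 or 16/16/20, since the actual split is not given.

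**Step 1: SD.** On the log scale, SD = sqrt(ln(1 + CV²)). Pooling the four variances by n − 1 gives a CV of about 42% for AUC (SD 0.403) and 59% for Cmax (SD 0.547).

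**Step 2: size of departure.** Let exposure be proportional to dose^b. The ratio of dose-normalised exposure at 15 versus 3.5 mg is then 4.29^(b − 1). A 1.5-fold ratio means b = 1 + ln 1.5/1.455 = 1.28; a 2-fold ratio means b = 1.48.

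**Step 3: power of the planned ANOVA.** Noncentrality λ = (b − 1)² × Sxx / SD², where Sxx is the sum over participants of (ln dose − mean ln dose)². At 8/8/8, Sxx = 8.478. For AUC and a 1.5-fold departure, λ = 0.2786² × 8.478 / 0.403² = 4.05. Against the F critical value 3.47 (2 and 21 df), power is 0.37. The other cells follow in the same way:

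| Active per level | 1.5-fold: AUC / Cmax | 2-fold: AUC / Cmax |
|---|---|---|
| 8/8/8 | 37% / 22% | 82% / 55% |
| 17/17/17 | 72% / 45% | >99% / 90% |
| 16/16/20 | 74% / 47% | >99% / 92% |

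At 8 per level, across the single-dose CVs of Table 3 (27% to 86%), power for a 1.5-fold departure runs from 73% down to 14%, and for 2-fold from 99% down to 32%. A fall of the same size (ratio 1/1.5 or 1/2) gives the same power.

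**Step 4: what a slope would show.** The 90% CI half-width for b is t × SD / sqrt(Sxx). At 8 per level (22 df, t = 1.717) it is 1.717 × 0.403 / 2.912 = 0.24 for AUC and 1.717 × 0.547 / 2.912 = 0.32 for Cmax. At 17 per level (Sxx = 18.015, t = 1.677) it is 0.16 and 0.22. For a log-linear 1.5-fold departure at 8 per level and the same alpha, the one-parameter slope test also has more power than the ANOVA: 49% against 37% for AUC, and about 29% against 22% for Cmax.

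**Step 5: illustration.** Rebuilding the same kind of ANOVA from the Table 3 summaries gives p = 0.21 for Cmax and p = 0.36 for AUC. The power-model slopes are 1.14 (90% CI 0.93 to 1.36) and 1.03 (0.87 to 1.19). Over a 4.29-fold dose range, the Cmax interval would mean a ratio between 4.29^(−0.07) = 0.90 and 4.29^0.36 = 1.69. This does not show non-proportionality. It shows how much room a non-significant p-value can leave.

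**The case against.** A reader might infer that a clearly non-proportional drug would usually be reported as proportional. The documents do not support that, for three reasons.

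First, a 2-fold departure is detected more often than not even with one cohort per level, and at least 90% of the time at 51 to 52 active. It is usually missed only at 8 per level with the single highest Cmax CV in Table 3. Eight per level is itself the minimum: Section 4.1 allows several cohorts per level, and Section 2.3 points to four cohorts across the two lower doses.

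Second, the plan nowhere says that non-significance will be reported as proportionality. The evaluation is exploratory and there are no formal hypotheses. The statement in Section 2.2.2.1, "Although the data showed moderate between-subject variability, no relevant departure from linearity was noted", describes another study and names no test.

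Third, the p-value is not the only evidence. CL/F and CLss/F are inverse dose-normalised exposures, and their geometric means will be presented, so a reader can see how AUC scales.

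All of this stands and limits the point. It does not remove it. The planned summaries contain no between-dose ratio with an interval, clearance covers AUC but not Cmax, and the modelling in Section 9.3.7 is optional. An exploratory aim without hypotheses is also a reason to estimate rather than to test.

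On accumulation the objection largely succeeds: the participant-and-day model on the log scale already yields the within-participant ratio, and only a commitment to report it is missing.

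**Conclusion.** The point holds as a matter of method and reporting. The planned test ignores dose order and comes with no between-dose estimate or interval, and its non-significance would not support proportionality. A moderate, 1.5-fold departure would be missed 63% (AUC) to 78% (Cmax) of the time at one cohort per level. With 51 to 52 active it would be missed about 26-28% of the time for AUC and 53-55% for Cmax. Large departures would mostly be found. More participants raise the power but do not turn a non-significant difference test into evidence of proportionality. The percentages rest on the assumed alpha, the pooled Table 3 variability and the assumed split across levels; the argument about non-significance does not.

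**What to change.** In Section 9.3.3, make the primary evaluation of dose proportionality a power model, ln(parameter) = a + b × ln(dose), for Cmax and AUC on Day 1 and at the last dose. Report b and the 15 versus 3.5 mg ratio of dose-normalised geometric means, each with a 90% CI. State that any conclusion on proportionality is drawn from the interval and not from a non-significant p-value. The ANOVA may stay as a supportive check, which is useful if the departure is confined to one dose and so not log-linear.

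For accumulation, add one sentence: from the participant-and-day model already planned, report the last-dose to Day 1 AUCtau geometric mean ratio with its 90% CI.

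The cost is wording only, with the same samples and data. The downside is a less favourable-looking statement of certainty: with expected half-widths for b of 0.24 to 0.32 at 8 per level, and 0.16 to 0.22 at about 17 per level, the report may have to say that proportionality is not settled.
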